A.3.1. SAGES I Cohort (N=560): Eligibility criteria included for initial enrollment: 1) age 70 years and older; 2) English speaking; 3) scheduled to undergo elective surgery; 4) scheduled at least 6 days prior to surgery to allow adequate time for the baseline assessment; 5) anticipated length of stay of at least 2 days; 6) planned general or regional anesthesia; and 7) living within 40 miles from study site. Eligible surgical procedures were: total hip or knee replacement, lumbar, cervical, or sacral laminectomy, lower extremity arterial bypass surgery, open abdominal aortic aneurysm repair, or colectomy. Exclusion criteria included: 1) evidence of dementia (dementia diagnosis, use of dementia drugs, or score <69 or education-adjusted equivalent on baseline Modified Mini-Mental State Test⁵³ 2) active delirium on initial cognitive testing: 3) hospitalization within 3 months prior to enrollment to minimize risk of recent delirium; 4) terminal condition with life expectancy < 6 months including terminal diagnoses such as metastatic cancer, pancreatic cancer, or receiving palliative care; 5) inability to perform cognitive tests due to legal blindness or severe deafness; 6) history of schizophrenia or psychosis; 7) current chemotherapy due to patient time burden; 8) documented history of alcohol abuse or withdrawal within last 6 months, and/or reporting more than 5 (4) drinks per day for men (women); 9) and inability to pass an assessment for capacity to provide informed consent. Initially 560 patients were enrolled; 6 patients were excluded due to baseline dementia. We will continue follow-up interviews with this cohort under the existing IRB protocol (2009P-000262).

A.3.2. SAGES I SELECT Sample Sub-group (N=148). A subset of selected participants from SAGES I will be invited to participate in lumbar puncture or amyloid-PET, MRI and Transcranial Magnetic Stimulation (TMS) procedures based on their delirium status. Delirium is defined by fulfillment of the Confusion Assessment Method¹ or chart criteria.⁵⁴ We will invite all SAGES I participants who developed delirium during the index hospitalization to participate, and we will enroll 74 participants into this subgroup. Next, we will enroll a sample of 74 patients who did not develop delirium or sub-

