Table 5. Description of the SAGES Neuropsychological Battery to assess cognitive functioning							
Test	Description	Domain(s) tested					
Trail-making Tests A and B	Participant must connect a sequence of alternating numbers and letters	Executive function, visual spatial function, processing speed					
Phonemic F-A-S Fluency	Participant must generate as many words in one minute as possible beginning with a given letter over three trials	Executive function, semantic memory, language					
Category Fluency	Participant must generate as many words in one minute as possible from a semantic category (e.g., "animals")	Executive function, semantic memory, language					
Visual Search and Attention Test	Four timed visual cancellation tasks where participant must cross out letters and symbols identical to a target	Executive, visual spatial function					
Hopkins Verbal Learning Test - Revised (HVLT-R)	A list of words is read to the participant, who is asked to repeat the list back over multiple learning and delayed recall trials	Verbal episodic memory					
Digit Span Forward/Backward	Participant is asked to repeat a string of digits forward and in reverse order	Sustained attention					
Boston Naming Test	Participant is presented with drawings of common objects, which then must be named correctly	Confrontation naming, language					
RBANS Digit Symbol Substitution	Using a key provided, the participant matches symbols to numbers as quickly as possible while being timed	Executive function, visual spatial function, processing speed					
AmNART	Participant is asked to pronounced words aloud presented to them on a piece of paper	Verbal IQ					

RBANS = Repeatable Battery for the Assessment of Neuropsychological Status AmNART = American National Adult Reading Test

A.4.5. Blood: (n=460 entire SAGES II cohort): We will collect blood from the entire SAGES II cohort participants at 4 time points: at the time of the baseline study assessment (baseline), on postoperative days 1, and 2 (POD1, POD2) and 1 month after surgery (100 ml total over 6 weeks). If a patient is discharged on the day of surgery, we will obtain blood on POD 1 or POD 2 in patient's discharge location. During the baseline and POD1 (or POD 0) assessments, three green top tubes (30 cc) will be

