A.4.9. Hospital assessments: The purpose of the hospital assessment is to monitor daily for development of delirium and to assess precipitating factors. We anticipate that all patients in the surgical group will be hospitalized. Automatic systems will be in place to notify the principal investigator immediately whenever an enrolled study patient is admitted to the BIDMC or BWH. Upon admission, the patient will be seen by the study team in the hospital (in-person or remotely via telephone or videoconference using an IRB approved platform like zoom or Starleaf), and will undergo daily 10-15 minute interviews including a cognitive screen, digit span test, CAM, DSI, MDAS ratings, and new delirium severity measures. Precipitating factors (e.g., infections, immobilization, surgical procedures, post-surgical complications) will be assessed by interview and review of the medical record using standardized, validated methods applied in our previous studies. The initial hospitalization during the study period will be considered the index hospitalization. The timing of follow-up will begin from the point of discharge. For study purposes readmission within 24 hours is considered a continuation of the hospital stay. Our study team is highly experienced in conducting such interviews in hospitalized persons, which will assist in assuring retention, as well as avoiding any interference with ongoing

medical care. If a patient is discharged on the day of surgery, we will conduct the POD 1 and/or POD 2 hospital interview in patient's discharge location or on the phone.

A.4.10. Post-hospitalization follow-up assessments: Several types of follow-up assessments will be conducted, as detailed below. These are all timed in relationship to the discharge date of the index hospitalization. Intercurrent illnesses and re-hospitalizations will be assessed at each follow-up time-point. If patients are hospitalized at the time of a scheduled follow-up assessment, we will wait for one month from hospital discharge to complete the follow-up assessment, to minimize the effects of acute illness on cognitive functioning. Some attrition is anticipated at each follow-up time point (due to mortality and losses to follow-up in this older population). These attrition rates are accounted for in all power calculations below.

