A.4.10.1. Face-to-face interview or phone interviews at two weeks (Delirium group only): The purpose of this 10-15 minute face-to-face or phone interview is to repeat the delirium assessment to better assess the duration and persistence of the index delirium episode. This interview will be conducted at 2 weeks after hospital admission in patients who had delirium at any time during the index hospitalization. This interview will be conducted in all settings of care, including hospital, home, assisted living, post-acute, or nursing home settings. We have extensive experience conducting interviews in all these settings, and the initial informed consent process will include these follow-up interviews. The two-week time period was selected for this interview, because previous work by our group has demonstrated the prognostic importance of the two week period.

A.4.10.2. Retest face-to-face interviews at one and two months follow-up (Retest 1 and 2): The purpose of these 45 minute face-to-face interviews is to repeat our delirium assessments and neuro-psychological test battery to test for both the persistence of delirium and to evaluate retest (learning) effects. All subjects will be interviewed, although only a subset will have developed delirium while hospitalized. The Retest 1 interview (at 1 month) will assess for immediate learning or retest effects, particularly in the patients with normal cognitive functioning. The Retest 2 interview (at 2 months) will assess for delayed learning effects, which our preliminary results suggest are likely to be present in the delirious patients. Patients will also be asked about any rehospitalizations or intercurrent illnesses. We will also ask participant and caregiver about their burden (distress) related to delirium.

A.4.10.3. Telephone follow-up interviews (2 weeks, 4, 9, 15, 21 and 27 months): The purpose of these 10-15 minute telephone interviews is to assess delirium status, functional status, intercurrent illnesses, rehospitalizations, or death. These interim telephone interviews are considered essential to maximize retention, and to conduct brief cognitive testing, discover unreported hospitalizations, and track deaths. As described above, the 2 week phone call will only be placed to patients who developed delirium in the hospital to assess duration of delirium.

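### In SAGES II, the days on which delirium can be detected depend on when the patient goes home, because no common set of postoperative interviews is fixed

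*Protocol*

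**What the plan says.** **Delirium.** Section A.4.9 gives each admitted SAGES II patient "daily 10-15 minute interviews including a cognitive screen, digit span test, CAM, DSI, MDAS ratings" and newer severity measures, in person or remotely. It states: "We anticipate that all patients in the surgical group will be hospitalized". For a patient discharged on the day of surgery, "we will conduct the POD 1 and/or POD 2 hospital interview in patient's discharge location or on the phone". No sentence covers a patient discharged on POD1. The Physical Setting part of section B7 places the daily interviews on the surgical units.

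**Later checks.** Section A.4.10.1 restricts the two-week assessment: "This interview will be conducted at 2 weeks after hospital admission in patients who had delirium at any time during the index hospitalization". The next delirium assessment of all patients is at one month, then at two months (A.4.10.2). Records of the index and later hospitalizations are abstracted for delirium (A.4.10.5), with support from text processing of the index chart (A.2.7).

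**Blood.** Section A.4.5 schedules draws on POD1 and POD2 for the whole cohort. For same-day discharges, however, "we will obtain blood on POD 1 or POD 2 in patient's discharge location", and the first postoperative draw is described loosely: "During the baseline and POD1 (or POD 0) assessments, three green top tubes (30 cc) will be".

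**Eligibility.** Section A.3.1 requires an "anticipated length of stay of at least 2 days", and section A.4 carries this over to SAGES II.

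**The concern.** Incident delirium is the outcome or the grouping variable in the SAGES II analyses. If interviews stop at discharge for some patients and continue for others, the chance of being found delirious depends on length of stay as well as on delirium itself. The eligibility criterion concerns the anticipated stay, and the protocol makes provision for same-day discharge in two places, so it expects some stays to be shorter than the schedule assumes.

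Discharge timing is unlikely to be random. Section A.4 adds abdominal, vascular and urologic operations to the SAGES I list, and CSF is collected only under spinal anesthesia (A.4.8). Procedure, anesthesia and health could therefore relate both to days observed and to which biomarker data exist. Under-detection unrelated to the marker costs power and dilutes contrasts. If it is related to the marker, the association itself can be biased, in either direction. In Project 1 the control variables include surgery type, but hospital-related factors are deliberately left out, so days observed would not be adjusted for.

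**Working it through.** **1. Coverage by discharge day, from the text**

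| Discharge | Delirium interview on POD1 | Delirium interview on POD2 | Two-week call if no delirium was found |
|---|---|---|---|
| Day of surgery | POD1, POD2 or both; one is enough | see POD1 | No |
| POD1 | Yes, as an inpatient day | No rule | No |
| POD2 or later | Yes | Yes | No |

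Patients who stay longer are also interviewed on each further inpatient day. The first two rows lack a guaranteed POD1-and-POD2 pair.

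**2. The plan's own power figure.** Project 5 Aim 1 (section B.1.3) expects 50 delirious and 130 non-delirious patients out of 180 by the end of hospitalization. It states 80% power for a standardized difference of 0.47. With a two-sided 0.05 test and the normal approximation:

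power = Φ(d × √(n1 × n0 / 180) − 1.96) = Φ(0.47 × √(50 × 130 / 180) − 1.96) = Φ(2.824 − 1.96) = 0.806.

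The stated figure reproduces.

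**3. Expected cases in the full cohort.** 0.24 × 460 = 110.4. (Project 2 in section B.1.3 writes 96 cases, which is 24% of 400, the size first used for power.)

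**4. Undetected cases.** The protocol gives neither the share leaving on POD0-1 (e) nor the share of their delirium that falls on an uninterviewed day (m). Both are assumptions here, with average delirium risk in early discharges. Undetected = 110.4 × e × m.

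- e = 5%, m = 20%: 110.4 × 0.05 × 0.20 = 1.1
- e = 10%, m = 40%: 110.4 × 0.10 × 0.40 = 4.4
- e = 25%, m = 20%: 110.4 × 0.25 × 0.20 = 5.5
- e = 50%, m = 40%: 110.4 × 0.50 × 0.40 = 22.1

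As shares of all cases these are 1%, 4%, 5% and 20%.

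**5. Effect on Project 5 Aim 1.** Assume that missed cases stay in the comparison group and that detection is unrelated to the marker. With a fraction S of cases found, n1 = 50S, n0 = 180 − n1, and the observed difference is d = 0.47 × (1 − (50 − n1)/n0).

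| Cases missed | n1 / n0 | d | Power |
|---|---|---|---|
| 0% | 50 / 130 | 0.470 | 0.81 |
| 5% | 47.5 / 132.5 | 0.461 | 0.78 |
| 10% | 45 / 135 | 0.453 | 0.75 |
| 20% | 40 / 140 | 0.436 | 0.68 |

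At 4% missed (48 / 132, d = 0.463), power is Φ(0.463 × √(48 × 132 / 180) − 1.96) = Φ(0.786) = 0.78.

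**The case against.** The strongest reply is that the affected group may be small. Enrollment requires an anticipated stay of at least two days, and A.4.9 expects all surgical patients to be hospitalized. If only 5-10% leave early, about 1 to 4 cases are at stake and power barely moves. This stands: the upper end of the range sits badly with the eligibility criterion and should not be read as a forecast.

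Several stronger readings are tempting, and the protocol does not support them.

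- A reader might infer that missed cases are classified as non-delirious. The protocol states no such rule. Section B.2.1 plans multiple imputation of outcomes where appropriate, and a classification rule may sit in an analysis plan that is not at hand. Imputation would help only if the patient is flagged as incompletely assessed; one negative interview may leave nothing flagged.
- A reader might infer that no later check exists. Everyone is assessed at one and two months, charts are reviewed, and a readmission within 24 hours continues the index stay. These checks would seldom reveal a short episode at home, but they exist.
- A reader might infer that POD1 discharges lose their POD2 blood. A.4.5 keeps that draw for the whole cohort and provides staff to collect it, and section B.5.2 allows it at home. Only same-day discharges have the either-or wording.
- A reader might infer that Project 2 hypothesis H1C depends on POD2 plasma from SAGES II. Section B.1.3 uses earlier POD2 findings only to choose an effect size and names no sampling day.
- A reader might extend the point to every aim, or to matched controls in Project 5. A.4.9 governs SAGES II only, so the SAGES I aims are untouched. The matching described in Project 5 belongs to Aim 3, in SAGES I; Aim 2 has only a comparison sample.

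**Conclusion.** The point holds for SAGES II analyses. The interview schedule, as written, makes the observation window for incident delirium depend on discharge day: same-day discharges can have a single postoperative interview, and POD1 discharges have no POD2 interview. The existing safeguards narrow this gap without closing it.

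The illustrative range in the working covers losses from negligible to material, and nothing in the protocol locates the trial within it. The power figures also assume that detection is unrelated to the marker. If discharge timing tracks the marker through procedure, anesthesia or health, bias is possible as well, and its size and direction cannot be determined from the protocol. The case for acting rests on the fact that an interview not held on the day cannot be recovered later, while holding it is cheap.

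**What to change.** 1. In A.4.9, require the CAM, DSI and digit-span interview on both POD1 and POD2 for every SAGES II patient regardless of discharge day, in person or by phone or video. Replace 'and/or' with 'and', and extend the rule to POD1 discharges.
2. Add a sensitivity analysis with delirium defined on the common POD1-POD2 window alone. This is needed because longer stays still bring further inpatient interviews, so the extra interview by itself does not equalize observation after POD2.
3. For same-day discharges, analyse plasma by the actual postoperative day of the draw. Do not make POD2 the mandatory single draw: Project 2 Aim 2 bases its power on pilot data from before surgery and POD1, so such a rule would give up POD1 samples.

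The cost is a short change to A.4.9 and at most one extra 10-15 minute call per early discharge, using the remote mode and staff already planned. The downside is a little more burden on patients just after they go home.

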A.4.8. Cerebrospinal fluid (CSF, up to n=460 entire SAGES II cohort): CSF collection will occur during spinal anesthesia for elective surgery. The procedure will be performed by the assigned anesthesia team led by experienced anesthesiologists in the operating room under standard monitoring, immediately before the planned operation. Using standard sterile technique and local anesthesia to the skin, the dural sac will be entered with an appropriately chosen Sprotte, Whitacre or Quincke needle 25-22G by the anesthesia team, under supervision of Drs. [name] (BWH), [name] (BWH-Faulkner), or [name] (BIDMC). After confirming intrathecal placement and adequate CSF flow, 2.0 ml of CSF will be collected; this amount is limited by feasibility and safety concerns of the anesthesiologists but is sufficient to accomplish the aims. Next, the anesthesiology team will inject local anesthetic for the surgical procedure through the same needle as per usual care. CSF will be centrifuged and managed in the same way as outlined above for the SAGES I SELECT cohort.

A.4.8.1. SAGES II subgroup participants for whom we could not collect CSF will be offered PET scans and using the same procedure as outlined above for the SAGES I SELECT subgroup

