B. Statistical Considerations

B.1. Sample Size Justification:

Our sample sizes were chosen based on an iterative process involving determining the size of the target population eligible, feasibility constraints, and then verifying adequate power to test the hypotheses across all of our proposed studies for Projects 1-5. Through these detailed considerations, and input from our expert statisticians, we have been able to verify adequate power to address all of our study aims with the proposed sample sizes for the SAGES I SELECT subsample (N=148), the SAGES II cohort (N=460) and the SAGES II subsample (N=180). Power has similarly been verified for all aims of each project. For SAGES II, approximately 50% of the cohort will be enrolled at BIDMC and 50% at BWH. The data, however, will be analyzed together. Computations allow for two-sided type-I error probability 0.05 and to take into account cumulative attrition consistent with our experience in this population. We use multiple imputation to account for missing data where appropriate.

B.1.2. Experimental design and sampling: general considerations

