Aim 1 Analyses: Aim 1 proposes to evaluate the relationship between baseline CSF AD biomarkers (CSF A $\beta_{42/40}$; t-tau; p-tau, tau/A β ratios, and NFL) and (1) the development of post-operative delirium; and (2) the pace of cognitive decline over 18-36 months following delirium. Hypothesis 1a posits that patients with abnormal CSF AD biomarker levels at baseline will have an increased risk of delirium following surgery, compared to patients with normal biomarker levels. This aim will be tested in the SAGES II cohort (N=460) with logistic regression models, with the occurrence of delirium as the outcome and biomarker positivity (abnormal level) as the main exposure variable. Control variables will include age, gender, nonwhite race, education, Charlson score, depression, impairment in any instrumental activity of daily living, surgery type, IQCODE, and baseline GCP score. To avoid overcontrolling for variables that might be intermediaries between delirium and its effect on cognitive trajectory,^{70,71} we will not adjust for hospital-related factors. Missing data will be addressed using multiple imputation (50 imputations) and the chained equations approach.⁷² Hypothesis 1b is a compound hypothesis statement that requires testing of 2 sub-hypotheses: (1) patients with abnormal CSF AD biomarker levels at baseline will have an increased risk for cognitive decline compared to those with normal biomarker levels, (2) the greatest decline will be observed in those with delirium and abnormal biomarker levels. This hypothesis will be tested with a generalized linear mixed effect modeling framework with a piecewise time basis describing the course of cognitive change by 3 timeperiods (acute period: pre-operative to 1 month; recovery period: 1-2 months; and long-term trajectory: >2-36 months), as we have done previously.^{22,26,63} The dependent variable is the GCP composite.^{55,73} The first part of this hypothesis, that biomarker positivity is related to cognitive decline, will be tested by regressing repeatedly observed cognition on time, biomarker positivity, and their interaction (with pre-specified control variables as described above). The hypothesis that biomarker positivity is associated with faster long-term decline is evaluated with the interaction of biomarker positivity and the long-term time trend. The second part of this hypothesis (the group with delirium and biomarker

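### The SAGES II biomarker models pool two hospital systems without a term for enrolling hospital, which leaves open a foreseeable and cheaply closed route to confounding

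*Protocol*

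**What the plan says.** Section B.1 (Sample Size Justification) says of SAGES II that "approximately 50% of the cohort will be enrolled at BIDMC and 50% at BWH. The data, however, will be analyzed together". It gives no method for handling hospital.

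Section B.2.3 (Project 1, Aim 1 Analyses) sets out the models. I use that section's labels: H1a is delirium on biomarker positivity, and H1b is the cognitive slope.

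- For H1a: "This aim will be tested in the SAGES II cohort (N=460) with logistic regression models".
- The covariates: "Control variables will include age, gender, nonwhite race, education, Charlson score, depression, impairment in any instrumental activity of daily living, surgery type". IQCODE and the baseline GCP score complete the list, which makes ten.
- For H1b the list is carried over as "pre-specified control variables as described above".
- Between the two comes the statement that "we will not adjust for hospital-related factors". The reason given is to avoid over-controlling for intermediaries between delirium and its effect on cognitive trajectory.

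Section A.4.8 places CSF collection with the anesthesia team assigned to the case, with a separate supervisor for BWH, BWH-Faulkner and BIDMC. It says that "the dural sac will be entered with an appropriately chosen Sprotte, Whitacre or Quincke needle 25-22G by the anesthesia team".

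Section B.2.1 gives a general rule for choosing covariates as possible confounders or effect modifiers and promises sensitivity analyses. It does not name hospital. Nothing elsewhere in the protocol stratifies, adjusts or tests by hospital.

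**The concern.** Enrolling hospital is a standard covariate when a cohort comes from more than one centre. Here it could plausibly be linked to both sides of the H1a comparison: to the exposure through local CSF collection or through who is referred there, and to the outcome through case mix or local care. It is settled before surgery, so the protocol's reason for leaving out intermediaries does not apply to it.

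If both links remain after the ten listed variables are in the model, patients from one hospital are over-represented among the biomarker-positive and also have more (or less) delirium. The pooled odds ratio then departs from the within-hospital value, and the H1a test no longer holds its 5% error rate. In principle the H1b interaction of biomarker with long-term time is open to the same problem if hospitals differ in positivity and in long-term slope.

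**Working it through.** **The plan's own figure.** The only detectable effect given for Project 1 Aim 1 (section B.1.3) is for the slope comparison: d = 0.28 to 0.33, with N = 400 and positivity 50% to 25%. Lehr's rule, d = 4/√(harmonic mean group size), reproduces it:

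- 50% positive: groups of 200 and 200, harmonic mean 200, d = 4/√200 = 0.283.
- 25% positive: groups of 100 and 300, harmonic mean 2×100×300/400 = 150, d = 4/√150 = 0.327.

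The figure is right and is not in dispute. It takes no account of hospital.

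**Inputs for the hospital question**

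- N = 460 split 230/230 (B.1), which assumes CSF from everyone.
- Delirium 24% overall (B.1.3, Project 2), about 0.24×460 = 110 events.
- Positivity in the range 25% to 50% (B.1.3, Project 1 Aim 1).
- Two-sided 5% error (B.1).
- Splits by hospital: assumed, because the protocol gives none. No covariates are included.

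**Formulas.** Let hospitals A and B have delirium risks pA, pB and positivity bA, bB, with no biomarker effect inside either hospital.

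- Delirium among positives: d1 = (pA·bA + pB·bB)/(bA + bB).
- Delirium among negatives: d0 = [pA(1−bA) + pB(1−bB)]/[(1−bA) + (1−bB)].
- Pooled OR = [d1/(1−d1)]/[d0/(1−d0)].
- With n1 = 230(bA+bB) and n0 = 460−n1, SE = √{1/[n1·d1(1−d1)] + 1/[n0·d0(1−d0)]}.
- With z = ln(OR)/SE, the false-positive rate is Φ(z−1.96) + Φ(−z−1.96).

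**Worked case: delirium 18%/30%, positivity 25%/43%**

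- d1 = (0.045 + 0.129)/0.68 = 0.2559.
- d0 = (0.135 + 0.171)/1.32 = 0.2318.
- OR = 0.3439/0.3018 = 1.14.
- n1 = 156.4, n0 = 303.6, SE = 0.228, z = 0.131/0.228 = 0.57.
- False-positive rate = 8.8%.

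If the pattern is reversed, so that the hospital with more positives has less delirium, d1 = (0.075 + 0.0774)/0.68 = 0.2241 and d0 = (0.225 + 0.1026)/1.32 = 0.2482. The OR is then 0.2888/0.3301 = 0.87, so the direction of any bias is unknown.

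**Results.** The simulated columns come from 2,000 logistic fits per row, without and with a hospital indicator. The Monte Carlo standard error at 5% is √(0.05×0.95/2000) = 0.5 percentage points.

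| Delirium A/B | Positivity A/B | Null OR, pooled | Error, formula | Error, simulated, no hospital | Error, simulated, with hospital | SE of log OR, without → with |
|---|---|---|---|---|---|---|
| 24/24% | 34/34% | 1.00 | 5.0% | 4.9% | 4.9% | 0.232 → 0.233 |
| 24/24% | 25/43% | 1.00 | 5.0% | 5.1% | 5.0% | 0.232 → 0.237 |
| 18/30% | 34/34% | 1.00 | 5.0% | 4.2% | 4.1% | 0.232 → 0.235 |
| 20/28% | 30/38% | 1.04 | 5.3% | 4.4% | 4.4% | 0.231 → 0.234 |
| 18/30% | 25/43% | 1.14 | 8.8% | 9.2% | 4.6% | 0.230 → 0.236 |
| 14/34% | 25/50% | 1.33 | 25.3% | 26.6% | 5.4% | 0.224 → 0.237 |

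With hospital in the model, the simulated null OR was 0.99 to 1.00 in every row. H1b was not simulated.

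**The case against.** The strongest reply is that this is detail for an analysis plan that is not at hand. The list is introduced with open wording, section B.2.1 allows confounders to be added, and pooling two hospitals is compatible with a hospital term. That stands in part, since nothing in the protocol rules the term out. But the protocol does more than stay silent: it names the covariates, calls them pre-specified when it reuses them, and leaves hospital out. Adding hospital after seeing results would look post hoc.

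The second reply is that the sites share eligibility criteria, standardized staff training, inter-rater checks on delirium assessment and one CSF handling procedure. The listed covariates, surgery type and baseline GCP among them, would also absorb much of any case-mix difference. This stands. The calculation has no covariates, so the gaps it assumes have to be read as what remains after adjustment. CSF will also not be obtained from all 460. For a given split, fewer samples leave the odds ratio unchanged but reduce the inflation of the error rate.

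Three stronger readings are tempting, and the protocol does not support them:

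- A reader might infer that the statement on hospital-related factors forbids a hospital term. Its stated reason concerns intermediaries, so it most likely means in-hospital course.
- A reader might infer that the hospitals do differ in CSF collection, case mix or care. Section A.4.8 shows local teams and a choice of needle. It does not show that needle choice follows hospital or that it changes biomarker levels.
- A reader might take the last row of the table as the expected error rate. It needs gaps of 20 points in delirium and 25 points in positivity, both surviving adjustment.

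**Conclusion.** The point holds as a foreseeable vulnerability and not as a demonstrated bias. The stated H1a and H1b models omit enrolling hospital from a cohort drawn about equally from two hospital systems. Confounding follows only if hospitals differ in both biomarker positivity (or CSF collection) and delirium after adjustment for the ten listed variables. Under the assumed splits it is zero when one variable differs alone, negligible for gaps of 8 points in each (OR 1.04, error 5.3%), and moderate for gaps of 12 points in delirium and 18 in positivity (OR 1.14, error about 9%). These sizes rest on equal hospitals, CSF from all 460, no covariates and no true effect. For H1b the concern is by analogy only, and no size can be given. What justifies acting is that the repair costs so little.

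**What to change.** - In section B.2.3 (Project 1, Aim 1 Analyses), add enrolling hospital as a fixed effect to the H1a logistic model and the H1b mixed model. Use BIDMC v BWH including Faulkner, or three levels if the Faulkner numbers allow.
- In H1b, also add a hospital-by-long-term-time term, because the hypothesis concerns the long-term slope.
- In the same section, say that the hospital-related factors left unadjusted are those of the in-hospital course, and that enrolling hospital is not one of them.
- In section B.1, note that the pooled analysis includes enrolling hospital as a covariate.

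Cost: H1a gains one parameter with two levels or two with three, against about 110 expected delirium events. H1b gains two (1 main effect + 1 interaction) or four (2 + 2). Interacting hospital with all three time periods would instead need up to six interaction parameters at three levels ((3−1)×3), which the hypothesis does not require. Enrolling hospital is known for every patient, and N does not change. In the two-level H1a simulations, the standard error of the biomarker log odds ratio rose from 0.232 to 0.233 when hospitals were alike and from 0.230 to 0.236 (2.6%) in the moderate case.
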